1.2 Study Hypothesis

The study hypothesis is that while a clinical decision rule more accurately risk-stratifies patients for AKI than creatinine screening, subsequent avoidance of exposure to contemporary contrast media agents does not alter overall AKI-risk. The alternative study hypothesis is that contrast media exposure is associated with an increased risk of AKI and the AKIrisk Score can be used to guide selective VQ imaging and reduce CIN in patients evaluated for PE in the emergency care setting.

This project will accomplish the following specific aims:

- 1) In 100 patients undergoing CTPA for suspected PE, test the accuracy of a AKIrisk Score <2 to predict a CIN-risk <10%.
- 2) Test if the use of acute-phase markers of renal dysfunction, Cystatin-C and/or NGAL, improves the predictive accuracy of the AKIrisk Score.
- 3) Compare the incidence of AKI consistent with CIN in 600 patients with suspected PE and a AKIrisk Score ≥2, randomized to standard CTPA (contrast media exposure) or VQ (unexposed control) imaging.

The outcomes of this research will 1) Validate effective methods of risk-stratifying patients for AKI-risk in the heterogeneous, real-world emergency care setting; and 2) Provide the rigorous evidence needed to change imaging practices and either a) more effectively prevent CIN OR b) Improve the utilization of imaging resources and avoid delays currently caused by unnecessary screening and prevention practices. These outcomes are central to future advances in AKI prevention in the emergency care setting and to optimizing current imaging practices; current time and resource consuming CIN-prevention methods characteristic of current clinical practice

will not change without prospective validation with a randomized, controlled trial.^{1, 3, 4} The specific translational impacts include 1) Quantification of the risk of AKI from contrast media exposure in the emergency care setting, 2) Validation of a clinical decision rule for the prediction of with either multi-cause AKI or CIN specifically, and 3) Vetting of two acute phase markers of renal dysfunction for use in the real-world, emergency care setting.

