We acknowledge that the primary outcome of CIN is likely to occur in patients that remain asymptomatic, as expected for the first stages of AKI. We do plan to measure and report patient-center, symptomatic, severe outcomes (see *Secondary Endpoints*) occurring within 1-year. Aside from our own preliminary data,^{7,11,20} there are no consistent, published, prospective data, with sufficient long-term follow-up,^{32,45} in the emergency care setting, or other comparable heterogeneous, ambulatory population (pre-exposure renal function ranging from normal to impaired). Moreover, there are no prospective, controlled data, in any setting, that can be used to adequately design (and determine the sample size for) a study primarily aimed at measuring the long-term, severe outcomes subsequent to CIN. Hence, we have focused on the first phase of AKI, CIN, as the primary outcome, and plan to use the data to inform future research quantifying the effect of selected contrast media exposure on the prevention of long-term severe outcomes subsequent to the development of CIN.

To determine sample size, we conservatively estimated an overall AKI rate of <20%. The sample size was determined based on a Chi-square test (two-tailed, 5% type I error). A sample size of 188 in the CTPA group (exposed) and 269 in the VQ group (unexposed) in each group will have 80% power to detect an absolute difference of 10%. Assuming up to 5% screening and randomization failures (patients assigned to VQ, but undergo CTPA imaging) and a 30% dropout rate,^{7,11,20,53,89} we will recruit 300 subjects per group. (nQuery 2014; Statistical Solutions©)

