Data Analyses Plan: We will select patients with low and moderate risk of PE and a normal chest radiograph. This selection strategy is designed to minimize "crossover" (randomized to VQ/no exposure, but go on to need a CTPA/exposure) (ACR Appropriateness Criteria® <https://www.guideline.gov/popups/printView.aspx?id=35135>, accessed 4/27/2016). Based published literature and our preliminary data, we conservatively anticipate that the crossover rate will be <5% using this selection strategy (see *Preliminary Data and Tables 3 and 4*).⁴⁹⁻⁵² Patients both the CTPA (exposure) and VQ (no exposure) groups will have the same post-test probabilities of PE and the risk of AKI (primary outcome) is not affected by the presence or absence of PE. For all analyses, patients will be considered in the groups to which they are randomly assigned. Statistical significance will be defined by the two-sided p-value <5% (SAS® v 9.1; SAS Institute Inc.).

Baseline Data Analyses: For each of two groups, we will be summarize continuous variables by group using descriptive statistics and categorical variables by frequency counts and percentages. Baseline clinical and demographic data will be compared between two groups to assess the effectiveness of the randomization. Dichotomous and ordinal variables will be examined using chi-square tests and continuous measures with Student's t-tests. Exploratory analysis will be performed to compute p-values which will be presented as an aid to evaluate the overall comparability of the two groups at baseline.

Missing Data Analysis: We anticipate a possible screening and randomization failures (5%)⁴⁹⁻⁵² and dropout (30%)^{7,11,20,53,89} and have adjusted the sample size. It is very unlikely that the dropout mechanism will depend on the unobserved outcome and we will compare the baseline covariates between the dropout and non-dropout groups for substantial differences. Under circumstances where compromise of power may be compromised by missing values, we will use a multiple imputation procedure to make use of all relevant observed data and assume that the data are Missing At Random (MAR), using the SAS® MI and MIANALYZE procedures.

Primary Outcome Analysis: For our primary aim, we will test the following hypothesis:

$$H_0 : |\varepsilon| \geq \delta \quad \text{vs.} \quad H_a : |\varepsilon| < \delta; \text{ where } \varepsilon = P_1 - P_2 \text{ and } \delta = 10\%$$

P_1 and P_2 are the true AKI rates in the CTPA and VQ groups, respectively.

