We will reject the null hypothesis and the two groups, CTPA and VQ, will be considered equivalent if

$$\frac{\hat{P}_1 - \hat{P}_2 - \delta}{\sqrt{\hat{P}_1(1 - \hat{P}_1)/n_1 + \hat{P}_2(1 - \hat{P}_2)/n_2}} < -z_{0.05} \quad \text{and} \quad \frac{\hat{P}_1 - \hat{P}_2 + \delta}{\sqrt{\hat{P}_1(1 - \hat{P}_1)/n_1 + \hat{P}_2(1 - \hat{P}_2)/n_2}} > z_{0.05}$$

If we reject the hypothesis of equivalency, we will conduct an analysis for a superior trial. Hence, for comparison with the dichotomous primary outcome, that is, whether a subject develops AKI at the 2-7 day follow-up, a logistic regression model will be used. Group comparisons will be adjusted for baseline covariates. To validate the decision rule in classifying subjects into a low-risk group we will: 1) Measure the AKI rate in the low-risk group (AKIRisk Score <2) with a desired margin of error. We assumed the upper limit of the one-way 95% confidence interval to be <10%, based on preliminary data, and prior literature.^{6,7} as such, we will compute the one-way 95% confidence interval using a Z test statistic; and 2) Compute sensitivity and specificity of the decision rule.

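### Superiority on the primary AKI endpoint is tested only when equivalence is not shown, so at low AKI rates a statistically significant increase can also meet the equivalence rule and be concluded only as equivalent

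*Combined protocol and SAP*

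**What the plan says.** Section 1.2 has two hypotheses. The first is that avoiding contrast does not alter AKI risk. For the other it says: "The alternative study hypothesis is that contrast media exposure is associated with an increased risk of AKI".

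Section 2.1 (Primary Outcome Analysis) sets the null as an absolute difference in AKI rates of at least 10 percentage points and the alternative as a smaller one. It gives two one-sided statistics, each compared with the 5% normal critical value, and says: "We will reject the null hypothesis and the two groups, CTPA and VQ, will be considered equivalent if" both inequalities hold. It continues: "If we reject the hypothesis of equivalency, we will conduct an analysis for a superior trial". The next sentence follows as a consequence: for the 2-7 day AKI outcome "a logistic regression model will be used", with adjustment for baseline covariates.

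The same section sets a general two-sided 5% significance level and sizes the trial on a difference test: "The sample size was determined based on a Chi-square test (two-tailed, 5% type I error"), with "80% power to detect an absolute difference of 10" percentage points. Where equivalence is concluded, the section gives no test of difference on the primary endpoint, no confidence interval for the difference, and no wording for a result that is both equivalent and significantly different.

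**The concern.** There are two defects.

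First, the trigger does not match the hypotheses. With non-equivalence as the null, the procedure either rejects non-equivalence or fails to. It has no outcome in which equivalence is rejected, so the sentence that starts the superiority analysis is not defined as written.

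Second, on the natural reading (equivalence not shown), the two analyses are treated as alternatives when they can both succeed. A 90% CI can lie inside ±10 points while the 95% CI excludes zero. The plan's only stated conclusion is then equivalence, although the same data show a statistically significant increase in AKI with contrast. That bears directly on the second hypothesis of section 1.2, in a trial meant to change imaging practice. How such a result is reported should be settled before the data are seen.

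**Working it through.** **1. The plan's own sample size.** Section 2.1 gives no arm rates, only an overall rate below 20% and a 10-point difference. Assume 19% vs 9% (mean 14%):

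n = [1.960·√(2·0.14·0.86) + 0.842·√(0.19·0.81 + 0.09·0.91)]² / 0.10² = 187.8, so 188 per arm.

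Then 188/0.70 = 268.6, so 269; and 269/0.95 = 283.2, so 284, which 300 covers. The stated 188 and 269 therefore reproduce as evaluable and dropout-inflated numbers per group for a chi-square difference test.

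**2. Evaluable patients.** Under the planned losses, 300 × 0.70 = 210 per arm, and 300 × 0.95 × 0.70 = 199.5, so 199. The figure 300 means no loss.

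**3. When both criteria can be met.** With d the observed difference and SE its standard error, equivalence needs d + 1.645·SE < 0.10 and significance needs d > 1.960·SE (ignoring the small difference between pooled and unpooled SE). Both hold only if SE < 0.10/(1.960 + 1.645) = 2.77 points. At 19% vs 9% with 199 per arm, SE = √[(0.1539 + 0.0819)/199] = 3.44 points, so the overlap is out of reach. At lower rates it is not.

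**4. A worked result.** Take 22/210 (10.5%) vs 11/210 (5.2%):

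- d = 5.24 points; SE = √[(0.1048·0.8952 + 0.0524·0.9476)/210] = 2.61 points.
- Equivalence statistics: (5.24 − 10)/2.61 = −1.82, below −1.645; (5.24 + 10)/2.61 = 5.83, above 1.645. Equivalence is concluded.
- 90% CI 0.9 to 9.5 points; 95% CI 0.1 to 10.4 points; chi-square p = 0.046.

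With 300 per arm, 36 vs 18 events (12% vs 6%) gives a 90% CI of 2.2 to 9.8 points and p = 0.010.

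**5. How often.** Joint probability of meeting the section 2.1 equivalence rule and a two-sided uncorrected chi-square p < 0.05, summed exactly over all pairs of binomial event counts:

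| True AKI rate, CTPA vs VQ | 199/arm | 210/arm | 300/arm (no loss) |
|---|---|---|---|
| 8% vs 4% | 20% | 23% | 47% |
| 10% vs 5% | 10% | 12% | 41% |
| 10% vs 6% | 6% | 7% | 30% |
| 12% vs 6% | 3% | 4% | 28% |
| 15% vs 6% | 0.5% | 0.6% | 7% |
| 19% vs 9% | 0.0% | 0.0% | 0.7% |
| 20% vs 15% | 0.0% | 0.0% | 0.0% |

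**6. Where the documents place the rates.** Some figures are low. Table 3 gives 6% AKI with VQ, and section 1.5 expects a lower VQ rate in this trial. Section 1.5 also reports 8-9% AKI in patients at low or moderate risk of PE, and the sample-size paragraph of section 2.2 puts the overall rate below 10%. Others are high for CTPA: an entry criterion of at least 20% risk, a positive predictive value of 27% for a score of 2 or more, 15% in CTPA patients generally, and 32% in Table 3.

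**The case against.** The strongest objection is that the affected scenarios are not the plan's central ones. Randomized patients are selected for high AKI risk, and Table 3 pairs its 6% for VQ with 32% for CTPA. At 27% vs 6% or 32% vs 6% the overlap is zero at every size examined. This stands: the problem depends on low rates in both arms, which the documents allow but do not predict. The larger probabilities also need complete follow-up, against a planned 30% dropout.

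A reader might infer that the rule hides the harm comparison whenever a real increase lies inside the margin. It does not. At 10% vs 5% with 199 per arm, 48% of trials are significant and 10% are significant and also equivalent, so about 79% of significant results (1 − 0.103/0.481) still reach the superiority analysis. At 12% vs 6% it is about 94%. Only at the lowest rates is the share large: at 8% vs 4%, about half of the significant results are also equivalent (0.196/0.392).

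A reader might also infer that a doubling of AKI would be published with nothing but the word equivalent. The documents do not say so. Nothing forbids reporting arm rates or an interval, and AKI by AKIN stage is compared as a safety and secondary outcome without this condition. That comparison is only a partial answer. It uses a different definition, and section 2.2 withholds from the adjudicators study creatinine values that are not in the medical record. The 95% CI in section 6.1 is a stopping rule at 15 points.

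Finally, a significant difference inside a prespecified margin is a legitimate equivalence result, not a contradiction. That is correct. What is missing is a rule for stating both findings.

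**Conclusion.** The point holds in a limited form. Section 2.1 makes the superiority analysis of the primary endpoint depend on equivalence not being shown, words that trigger in a way the stated null cannot produce, and gives no conclusion for results that meet both criteria.

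Under the planned losses the overlap is a realistic possibility (roughly 3% to 23%) if AKI is about 4-6% with VQ and 8-12% with CTPA. It is negligible near the rates that reproduce the sample size and at the CTPA rates in the preliminary data.

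The probabilities rest on assumed true rates and on an unadjusted chi-square test in place of the planned adjusted logistic model. Near the boundary the choice of test matters: 22 vs 11 of 210 has a Fisher exact p of 0.068. This is a flaw in the decision rule that should be corrected; it does not undermine the design.

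**What to change.** Replace the trigger sentence in section 2.1 with wording such as:

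> Whether or not equivalence is concluded, the risk difference with 90% and 95% CIs and the two-sided superiority analysis will be reported; if both criteria are met, the conclusion will state a statistically significant difference smaller than 10 points.

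Wherever the trigger is still referred to, speak of failing to conclude equivalence rather than of rejecting it.

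The cost is a change of text. The sample size is unaffected. No alpha adjustment is needed: a true difference of at least 10 points and a true difference of zero cannot both hold, so at most one of the two nulls is true, and each is tested at its own nominal 5% level.

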In the same prospective cohort, the PI has also tested the prognostic accuracy of two emerging biomarkers of acute-phase renal dysfunction in her CT cohort, Neutrophil Gelatinase-Associated Lipocalin (NGAL) and Cystatin-C (eGFR_{CYS}, expressed as eGFR calculated using Cystatin-C¹⁷), alone and in combination with the AKIrisk Score. (Table 2.)^{9,10}

As proof of concept, preliminary data also indicate that exposure to contrast media with CTPA in associated with an increased risk of AKI: The PI examined retrospective data for 100 randomly selected patients (50 male and 50 female) at low or moderate risk of PE, with VQ imaging for suspected PE and 100 matched controls (age, gender, Black race, and eGFR_{SCr}) with CTPA imaging between January and December of 2014.

Table 2. Comparison of the predictive accuracy for contrast-induced nephropathy (CIN) of Neutrophil Gelatinase-Associated Lipocalin (NGAL, alone and when included in the AKIrisk Score) and Cystatin-C (expressed as eGFR_{CYS}) to creatinine (expressed as eGFR_{SCr}).

Factor	Threshold	AUROC	Sensitivity	Specificity
eGFR _{SCr}	≤ 60 ml/min/m ²	0.55 (0.47 to 0.63)	13% (5 to 23%)	87% (83 to 90%)
NGAL	≥ 100 mg/dL	0.68 (0.60 to 0.75)	80% (64 to 91%)	63% (57 to 69%)
NGAL AKIrisk Score*	≥ 3 points	0.82 (0.75 to 0.89)	90% (76 to 97%)	60% (54 to 65%)
eGFR _{CYS} †	≤ 60 ml/min/m ²	0.76 (0.56 to 0.95)	65% (52 to 77%)	88% (84 to 90%)

*NGAL AKIrisk Score: NGAL ≥ 100 ng/dL 3 points, and 1 point each for age ≥ 50 years, diastolic hypertension ≥ 100 mmHg, and diabetes mellitus.

†There was no improvement in prognostic accuracy when eGFR_{CYS} was combined with the AKIrisk Score.

Dialysis dependent patients and renal transplant patients were excluded, as were patients who were exposed to intravascular contrast media, within 30 days prior to, or within 7 days following, the selected PE imaging study (VQ or CTPA). Findings are summarized in Table 3. Importantly, the rate of intermediate risk VQ was only 3% and the detection rate of acute PE by VQ was not lower than CTPA. Because physician assessment of increased risk of CIN is the primary reason that patients undergo VQ imaging rather than CTPA,⁶ it is not surprising that a larger proportion of patients in the VQ group had a AKIrisk Score ≥ 2 . Because VQ is usually reserved for patients at the upper-limit of overall risk AKI (CIN and other additional causes), we expect that the incidence of AKI in the

[figure not shown]

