Sample Size We will use a prospective validation study design for the previously derived decision rule (AKIrisk Score), classifying subjects into low AKI-risk group. We will recruit 100 subjects undergoing CTPA with an AKIrisk Score <2 . Since the overall AKI rate in our patient population of interest is $<10\%$ (see *Preliminary Data*), the group of subjects with AKIrisk Score <2 will have much lower AKI rate. Assuming 5% AKI rate in this low risk group, the upper limit of one way 95% confidence interval will be $\leq 9.3\%$ with a sample size of 100 (adjusted for dropout and screening failures).

Secondary Outcome Analysis: We will measure several secondary outcomes of which almost all are dichotomous (e.g. death, renal failure, stroke and/or other acute arterial vascular events). We will use a logistic regression model including the baseline covariates in the model. In case of rare events, we will use an exact logistic regression analysis. For the change in continuous outcomes, we will use ANCOVA model including the baseline covariates. Using similar analyses, we will compare baseline outcomes between enrolled subjects and subjects who will meet the inclusion criteria but decline participation in the study. Finally, we will compare outcomes of patients, relative to the AKIrisk Score, and we will compare outcomes and demographic data of those who enroll versus those who meet inclusion but decline participation to assess for possible bias induced by the informed consent process.⁸⁴

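### The only numerical target for validating the AKIrisk Score tests absolute rule-out risk, not discrimination, and no planned analysis compares the score with creatinine screening

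*Combined protocol and SAP*

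**What the plan says.** Section 1.2 (Study Hypothesis) begins with the proposition that "a clinical decision rule more accurately risk-stratifies patients for AKI than creatinine screening". Aim 1 in the same section is to "test the accuracy of a AKIrisk Score <2 to predict a CIN-risk <10" percent in 100 patients undergoing CTPA.

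Section 2.1 (Primary Outcome Analysis) gives two validation steps. The first measures the AKI rate in the score <2 group: "We assumed the upper limit of the one-way 95% confidence interval to be <10%, based on preliminary data, and prior literature", and "we will compute the one-way 95% confidence interval using a Z test statistic". The second is "Compute sensitivity and specificity of the decision rule", with no target value.

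Section 2.2 (Sample Size) sizes the group on the same limit: "Assuming 5% AKI rate in this low risk group", the one-sided 95% upper limit is put at 9.3% or less with 100 patients. It explains the low assumed rate thus: "Since the overall AKI rate in our patient population of interest is $<10" percent. Section 2.2 also says that outcomes will be compared relative to the score, without naming a statistic.

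Section 4.2 names the validation data: the score <2 patients together with the score ≥2 patients randomized to CTPA. Section 5.1 provides for a baseline creatinine.

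**The concern.** An upper limit on the AKI rate in score <2 patients answers one question: is this group's risk low? It does not show that score ≥2 patients are at higher risk, or that the score sorts patients better than creatinine. If overall AKI is uncommon, a score unrelated to AKI can meet the target. If AKI is common, a score that works as it did in derivation can miss it.

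Two conclusions are at stake. One is that the score risk-stratifies patients, for which no criterion is set. The other is that it does so more accurately than creatinine screening, for which no analysis is planned. For context, Table 2 in section 1.5 gives eGFR ≤60 an AUROC, sensitivity and specificity of "0.55 (0.47 to 0.63) 13% (5 to 23%) 87% (83 to 90" percent), so the creatinine comparator looked weak in the preliminary data. The trial is meant to confirm that prospectively, but the plan does not say how.

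**Working it through.** **Inputs.** Upper-limit target of 10%, one-sided 95%, Z method (section 2.1). Assumed low-risk AKI rate 5%, 100 patients (section 2.2). Dropout 30% (section 2.1). Derivation sensitivity 56%, specificity 81% and positive predictive value 27% for score ≥2 (section 1.5). The number evaluable is not stated, so both n = 100 and n = 70 (100 × 0.70) are shown.

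**1. The plan's own figure.** Upper limit = p + 1.645 × √(p(1−p)/n). With p = 0.05 and n = 70: 0.05 + 1.645 × √(0.0475/70) = 0.0929. The stated 9.3% reproduces with 70 evaluable patients; n = 100 gives 8.6%.

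**2. What meets the target.** The largest event counts with an upper limit below 10% are 6 of 100 (6.0%; limit 9.9%) and 3 of 70 (4.3%; limit 8.3%). Seven of 100 gives 11.2% and four of 70 gives 10.3%.

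**3. Chance of meeting it.** This is the binomial probability of at most 6 of 100, or at most 3 of 70. For a score with no discrimination, the low-risk rate equals the overall rate p. For a score with the derivation accuracy, the low-risk rate is 0.44p / [0.44p + 0.81(1−p)]; at p = 0.10 this is 0.044/(0.044 + 0.729) = 5.7%. The overall rates are assumptions within the 5 to 25% that section 1.4 cites.

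| Overall AKI rate | No discrimination, n = 100 / 70 | Low-risk rate, derivation accuracy | Derivation accuracy, n = 100 / 70 |
|---|---|---|---|
| 5% | 77% / 53% | 2.8% | 98% / 87% |
| 8.5% | 24% / 14% | 4.8% | 79% / 56% |
| 10% | 12% / 7% | 5.7% | 66% / 43% |
| 15% | 0.5% / 0.5% | 8.7% | 22% / 13% |

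**4. The rate implied by the derivation figures.** Prevalence odds = (0.27/0.73) × (0.19/0.56) = 0.1255, so the overall rate is about 11.1%. The score <2 rate is then 0.44 × 0.1115 / (0.44 × 0.1115 + 0.81 × 0.8885) = 6.4%. At 6.4% the target is met 54% (n = 100) or 34% (n = 70) of the time.

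**5. The overall rates side by side.** Section 2.2 (Sample Size): below 10%. Section 1.5: over 10% in all CT patients, 15% with CTPA, and 8 to 9% in a subset at low or moderate PE risk. Section 1.1: more than 15% after CTPA. Section 2.1 (sample size for the randomized comparison): below 20%. The last is not logically incompatible with the first, but it is a different planning value, and section 2.2 does not say exactly which population it means.

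**6. Effect of enrolling by score.** About 300 CTPA patients will have a score ≥2 and 100 a score <2. In derivation the share with a score ≥2 was 0.56 × 0.1115 + 0.19 × 0.8885 = 23%. With risks of 27% and 6.4%, expected events are 81 and 6.4. Unweighted sensitivity is 81/87.4 = 93%, and specificity is 93.6/(219 + 93.6) = 30%. The same score that gave 56% and 81% would appear to give 93% and 30%.

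**The case against.** The strongest case is that the 10% limit is the right analysis for the question Aim 1 asks. Whether score <2 marks a risk below 10% is an absolute rule-out question, and an upper confidence limit answers it. Section 2.1 words the limit as an assumption tied to a desired margin of error, and section 2.2 uses it to size the group, so it can be read as precision planning. Sensitivity and specificity are also planned, and they need AKI outcomes in score ≥2 patients. A useless score would show itself there, because the two would sum to about 100%. Section 4.2 already names a contrast-exposed validation set. All of this stands. What it leaves open is that nothing ties those statistics to a conclusion, and none of them involves creatinine.

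A reader might infer more than the documents support, in three ways:

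- **That the population already meets the target, so a useless score would be declared validated.** The target is on the upper limit, not the rate. At an observed 9% the upper limit is 13.7% (n = 100) or 14.6% (n = 70). The below-10% figure is also contradicted by sections 1.1 and 1.5.
- **That the target responds to the base rate and not to the score.** At every matched rate in the table, the score with derivation accuracy meets it more often, for example 79% / 56% against 24% / 14% at 8.5%. The target depends on both.
- **That patients negative on creatinine screening have exactly the overall AKI rate.** This follows only from the point estimates (13% + 87% = 100%). The intervals in Table 2 are wide: sensitivity 5 to 23%, specificity 83 to 90%.

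**Conclusion.** The concern holds in a limited form. The one numerical validation target measures absolute risk in score <2 patients. No criterion is set for sensitivity, specificity, AUROC or a high-versus-low difference, and no planned analysis tests the hypothesised advantage over creatinine. The missing creatinine comparison is the firmer part, because it rests on the text alone.

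The risk of a misleading positive depends on the overall AKI rate: substantial near 5% (77% / 53%), modest at 10% (12% / 7%) and negligible at 15% (about 0.5%). The risk of missing the target with a score that works as derived is considerable at 10% (34% / 57%) and high at 15% (78% / 87%). These figures assume the Z limit as planned, 70 to 100 evaluable patients, and the derivation sensitivity and specificity. Because the protocol gives conflicting overall rates, the documents do not settle which row of the table applies. The point concerns the validation claims and does not touch the randomized comparison of CTPA with VQ.

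**What to change.** Keep the one-sided 95% upper limit below 10% as the Aim 1 rule-out test. It should not be replaced: at a 20% overall rate the score <2 group would have about 12% AKI (0.088/(0.088 + 0.648)), and a high-versus-low contrast alone would still succeed.

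In the section 4.2 validation set (CTPA patients only), add:

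1. **The AKI risk difference between score ≥2 and score <2, with its 95% confidence interval.** Require a lower limit above 0 before stating that the score risk-stratifies. With 210 and 70 evaluable patients and the derivation accuracy, a two-sided 5% pooled z-test has power 81%, 96% and 98% at overall rates of 5%, 8.5% and 10%. A score-type interval matches that test.
2. **A paired comparison of the score with baseline eGFR (≤60 and continuous) for the same AKI outcome in the same patients.** Only this should support a claim of greater accuracy than creatinine screening.

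Weight sensitivity, specificity and comparison 2 to the score mix of screened patients. If screening scores are not kept, state an assumed mix and show the range.

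Reconcile the overall AKI rates in sections 1.1, 1.5, 2.1 and 2.2 and state the population for each. Align the Précis, which also includes the unexposed controls in the validation, with section 4.2.

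The cost is SAP wording, two further analyses and score counts from the screening log, with no extra patients. The validation claim becomes harder to make. The power of comparison 2 has not been worked out and should be stated before the data are seen.
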